5.5 Module 3 Specific Exclusion Criteria

Participants are excluded from Module 3 (RXC004 + pembrolizumab) if any of the following criteria apply:

14. Patients with any contraindication to the use of pembrolizumab as per approved label (Summary of Product Characteristics or equivalent).
15. Has received prior therapy with an anti-PD-1, anti-PD-L1, or anti-PD-L2 agent or with an agent directed to another stimulatory or co-inhibitory T-cell receptor (e.g., CTLA-4, OX 40, CD137), and was discontinued from that treatment due to a Grade 3 or higher irAE.

16. Has received prior radiotherapy within 2 weeks of start of study treatment or have had a history of radiation pneumonitis. [Note: Participants must have recovered from all radiation-related toxicities and not require corticosteroids. A 1-week washout is permitted for palliative radiation (\leq 2 weeks of radiotherapy) to non-central nervous system (CNS) disease.]
17. Has a diagnosis of immunodeficiency or is receiving chronic systemic steroid therapy (in dosing exceeding 10 mg daily of prednisone equivalent) or any other form of immunosuppressive therapy within 7 days prior the first dose of pembrolizumab in this study.
18. Has severe hypersensitivity (\geq Grade 3) to pembrolizumab and/or any of its excipients.
19. Has an active autoimmune disease that has required systemic treatment in past 2 years (i.e., with use of disease modifying agents, corticosteroids or immunosuppressive drugs). Replacement therapy (e.g., thyroxine, insulin, or physiologic corticosteroid replacement therapy for adrenal or pituitary insufficiency) is not considered a form of systemic treatment and is allowed.
20. Has a history of (non-infectious) pneumonitis / interstitial lung disease that required steroids or has current pneumonitis / interstitial lung disease.
21. Has an active infection requiring systemic therapy.
22. Patients with a history of allogeneic tissue/solid organ transplant.
23. Patients with active infections, including tuberculosis, HIV, HBV, or HCV. Patients with a resolved HBV infection (defined as presence of hepatitis B core antibody [HBcAb] and absence of HBV surface antigen [HBsAg] or negative on PCR for HBV DNA) are eligible. Patients positive for HCV antibody are eligible only if PCR is negative for HCV RNA.

5.6 Lifestyle Considerations

5.6.1 Contraception

1. Women must be 1 year post-menopausal, surgically sterile or agree to using enhanced contraceptive measures for the duration of the study, from the time of treatment initiation, and for 5 months after the last dose of study drug, with all male sexual partners. Highly effective methods of contraception must be used, which include having a vasectomised partner, sexual abstinence (defined as refraining from heterosexual intercourse during the study and for 5 months after the last dose of study drug. The reliability of sexual abstinence needs to be evaluated by the Investigator, in relation to the duration of the study and the preferred/usual lifestyle of the patient), or one of the following: hormonal contraceptives which inhibit ovulation (oral, injectable, transdermal, intravaginal or implants), Intrauterine Device (IUD), Intrauterine Hormone-releasing System (IUS) (e.g., Mirena), or bilateral tubal occlusion.

2. Men must use a condom (with spermicide) during the study, and for 5 months after the last dose of study drug, with all sexual partners.
3. Men must not donate sperm for 5 months after the last dose of study drug.

5.6.2 Meals and Dietary Restrictions

Patients must fast (water to drink only) from at least 2 hours prior to taking a dose to at least 1-hour post-dose for all doses. Patients should abstain from eating large amounts of grapefruit and Seville oranges (and other products containing these fruits e.g. grapefruit juice or marmalade) during the study (e.g., no more than a small glass of grapefruit juice (120 mL) or half a grapefruit or 1-2 teaspoons (15g) of Seville orange marmalade daily).

For participants in Module 3, no additional meal or dietary restrictions are required with regard to pembrolizumab study treatment, unless modifications are required to manage an AE such as diarrhoea, nausea, or vomiting.

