RXC004 has not shown the potential to induce or inhibit CYP enzymes or transporters at the dose to be investigated in this study but it is exclusively metabolised by CYP3A4 and as such has the potential for DDI with potent CYP inhibitors (which could increase levels of RXC004, leading to a higher risk of AEs). As such, strong and moderate CYP3A4 inhibitors are contraindicated in this protocol (see Appendix E). Patients with pancreatic and biliary tract cancers commonly require co-medications with analgesics, antacids, antibiotics, anti-emetics, anti-diabetic agents, anti-diarrhoeal drugs, anti-depressants, anxiolytic drugs, pancreatic enzyme replacements and other nutritional supplements. Some agents within these classes are CYP3A4 inhibitors.

Appendix E highlights the CYP 3A4 inhibitors which are also likely to be commonly used in CRC patients. These drugs should be avoided, and alternatives used wherever possible. If it is

not possible to use an alternative (e.g. if a specific antibiotic or anti-fungal treatment is needed), RXC004 should be interrupted.

Potential for QTc Prolongation

Based on pre-clinical data (hERG assay, ECG monitoring in 28-day GLP toxicology studies), RXC004 is not considered to have a significant potential to prolong the QTc interval. RXC004 did not lead to cardiac AEs including arrhythmias, or syncope in the Phase 1 study.

TriPLICATE ECGs will be collected in this other RXC004 studies so that the potential for QTc prolongation can be explored in future as part of a population PK analysis.

Potential for an Effect of Food on RXC004 Exposure

It is not yet known whether food may increase or decrease the exposure of RXC004. Until such data are generated, RXC004 must be given in a fasted state, as described in Section 5.6.2, and this is explained to patients in the Information Sheet.

Potential for Risks in Specific Patient Populations

A preliminary analysis of data from the Phase 1 study showed no effect of age, sex, BMI or race on RXC004 PK.

Pre-clinical development showed that RXC004 is exclusively metabolised by CYP3A4 and there was no renal clearance of RXC004. However, there is currently no information on the clearance of potential human metabolites of RXC004. While data are limited, the study inclusion criteria will restrict the use of RXC004 to patients with adequate renal and hepatic function.

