3mg QD	4	4	Non-tolerated dose RXC004 related AEs ≥ CTCAE G2 (4/4 patients); G2 Fatigue (1/4 patients) ^b G2 Nausea (1/4 patients) ^b G2 Constipation (1/4 patients) ^b G2 Anorexia (2/4 patients) ^b G2 Colitis (2/4 patients) ^b [DLT] G2 Dysgeusia (1/4 patients) ^b G3 Enteritis (1/4 patients) [DLT] G2 hyponatremia (1/4 patients) G2 Humerus fracture (1/4 patients) G5 Subdural Hematoma (1/4 patients)
10mg QD	1	1	Non-tolerated dose One DLT – G3 Diarrhoea. G3 proctitis, G2 enterocolitis, dysgeusia and fragility bone fractures also reported for this patient

^a The DLT assessment period runs from the start of dosing with RXC004 (Cycle 0 Day 1) up to Cycle 1 Day 21. To be evaluable for DLT assessment patient must had received at least 66% of the intended dose of RXC004 during Cycle 1 or have experienced a DLT event in the assessment period

^b The start date of one or more events was outside of the DLT period. However, AEs occurring in Cycle 2 and beyond which meet the definition of a DLT or are considered clinically significant may also be considered by the Safety Review Committee, when making dose escalation decisions.

AE, adverse event; DLT, dose-limiting toxicity; QD, once daily.

No DLTs were observed in the patients dosed in the first three cohorts since the study was restarted (RXC004 doses from 0.5mg to 2mg). At the 3mg dose level, two DLTs of colitis and enteritis were observed in 2/4 (50%) evaluable patients, which led to the SRC declaring RXC004 3 mg QD as non-tolerated.

Denosumab (XGEVA™ - 120 mg s.c. once every month) was administered prophylactically from Cycle 0 to all patients from cohort 3 (1.5mg RXC004) onwards, to maximise bone safety.

A summary of the TEAEs, regardless of causality, reported for RXC004 monotherapy in the Phase 1 study RXC004/0001 (NCT03447470) up to 30 July 2021 is included in Table 2 below.

Table 2 Summary of TEAEs (Phase 1 study RXC004/0001, monotherapy)

Number of patients with TEAE	0.5 mg; N=4 n (%)	1.0 mg; N=3 n (%)	1.5 mg; N=7 n (%)	2.0 mg; N=6 n (%)	3.0 mg; N=4 n (%)	10.0 mg; N=1 n (%)	Overall; N=25 n (%)
Any TEAE	4 (100)	3 (100)	7 (100)	6 (100)	4 (100)	1 (100)	25 (100)
Any Treatment-Related TEAE	4 (100)	3 (100)	5 (71)	5 (83)	4 (100)	1 (100)	22 (88)
TEAE \geq Grade 3	0 (0)	1 (33)	6 (86)	1 (17)	3 (75)	1 (100)	12 (48)
Treatment-Related TEAE \geq Grade 3	0 (0)	0 (0)	2 (29)	1 (17)	1 (25)	1 (100)	5 (20)
Serious TEAE	0 (0)	1 (33)	5 (71)	1 (17)	3 (75)	1 (100)	11 (44)

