5.6.3 Concomitant Treatments

5.6.3.1 Prohibited and Restricted Medications (Modules 1, 2, and 3)

Medications or vaccinations specifically prohibited in the exclusion criteria are not allowed during the ongoing trial. If there is a clinical indication for any medication or vaccination specifically prohibited during the trial, discontinuation from study intervention or vaccination may be required. The investigator is to discuss prohibited medication/vaccination with the Sponsor's Clinical Director. The final decision on any supportive therapy or vaccination rests with the investigator and/or the participant's primary physician. However, the decision to continue the participant on study treatment requires the mutual agreement of the investigator, the Sponsor, and the participant.

The following concomitant medication is prohibited:

1. The use of any natural/herbal products or other 'folk remedies'.
2. No other chemotherapy, or other anticancer therapy, including radiation therapy (except local treatment to a symptomatic solitary lesion), immunotherapy, and hormonal therapy (contraception and hormone replacement therapy is acceptable), or other investigational product is permitted other than the study treatments.
3. The use of some CYP3A4 inhibitors and inducers should be restricted prior to first dose of study treatment and throughout the study treatment, as RXC004 is observed to be exclusively metabolised by CYP3A4. For a list of prohibited CYP3A4 inhibitors and inducers and details of restrictions prior to the first dose of study treatment, please refer to Appendix E.

4. Drugs that are immunosuppressive or may cause secondary osteoporosis should not be administered (e.g. corticosteroids, pioglitazone or rosiglitazone). The following exceptions are allowed:
 - Use of immunosuppressive medication for the management of colitis events (per Appendix K), or pembrolizumab-related AEs (please refer to Appendix L).
 - Steroids required for the management of RXC004- or pembrolizumab-related AEs should be tapered to prednisolone \leq 10 mg/day equivalent, before re-starting study treatment.
 - Systemic glucocorticoids when used for the following purposes:
 - To modulate symptoms of an AE that is suspected to have an immunologic aetiology
 - For the prevention of emesis
 - To premedicate for IV contrast allergies
 - To treat chronic obstructive pulmonary disease (COPD) exacerbations (only short-term oral or IV use in doses $>$ 10 mg/day prednisone equivalent)

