6.4 Reporting of Concomitant Therapy

Any medication or vaccine (including over-the-counter or prescription medicines, vitamins, and/or herbal supplements) that the participant is receiving at the time of enrolment or receives during the study must be recorded along with:

- Reason for use
- Dates of administration including start and end dates

- Dosage information including dose and frequency

Concomitant medication may be given as medically indicated with the exception of prohibited concomitant medication (Section 5.6.3 and Appendix E).

The timeframe for reporting concomitant therapy is from Screening (within 28 days prior to first dose of study treatment) up to 30 days after last dose of RXC004, and up to 90 days after last dose of pembrolizumab in Module 3. The Medical Monitor should be contacted if there are any questions regarding concomitant or prior therapy.

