Appendix E Prohibited CYP3A4 Inhibitors and Inducers

CYP 3A4 Inhibitors [Bold text denotes commonly used co-medications in patients with pancreatic or biliary tract cancers]	CYP 3A4 Inducers [None of these drugs are commonly used co-medications in patients with pancreatic or biliary tract cancers]

Strong CYP 3A4 Inhibitors Concomitant use of these drugs has the potential to increase the exposure of RXC004 >5-fold These agents must not be given within 14 days of first dose of study treatment
 
Boceprevir, cobicistat, danoprevir and ritonavir, elvitegravir and ritonavir, grapefruit juice, indinavir and ritonavir, itraconazole, ketoconazole, lopinavir and ritonavir, paritaprevir and ritonavir and (ombitasvir and/or dasabuvir), posaconazole, ritonavir, saquinavir and ritonavir, telaprevir, tipranavir and ritonavir, troleandomycin, voriconazole, clarithromycin, idelalisib, nefazodone, nelfinavir.
	
Strong CYP 3A4 Inducers Concomitant use of these drugs has the potential to decrease the exposure of RXC004 by >80% These agents must not be given within 14 days of first dose of study treatment
 
Aptalutamide, carbamazepine, enzalutamide, mitotane, phenytoin, rifampin, St. John's wort.

Moderate CYP3A4 Inhibitors Concomitant use of these drugs has the potential to increase the exposure of RXC004 by 2-5-fold A washout period of 14 days is recommended and a minimum washout period of 5 half-lives (See SMPC or USPI) is required before first dose of study treatment.
 
Aprepitant, , conivaptan, crizotinib, cyclosporine, diltiazem, dronedarone, erythromycin, fluconazole, fluvoxamine, imatinib, tosipam, verapamil lansoprazole.
	
Moderate CYP 3A4 Inducers Concomitant use of these drugs has the potential to decrease the exposure of RXC004 by 60-80% A washout period of 14 days is recommended and a minimum washout period of 5 half-lives (See SMPC or USPI) is required before first dose of study treatment.
 
Bosentan, efavirenz, etravirine, phenobarbital, primidone.

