
Weak CYP3A4 Inhibitors These are not prohibited but should be used with caution as they may increase the exposure of RXC004 by 1.25 -2- fold
 
Chlorzoxazone, cilostazol, cimetidine, clotrimazole, fosaprepitant, istradefylline, ivacaftor, lomitapide, ranitidine, ranolazine, ticagrelor, omeprazole
	
Weak CYP3A4 Inducers These drugs are not prohibited- they have the potential to decrease the exposure of RXC004 by 20-50% which is within the scope of the dose reduction allowances
 
Armodafinil, modafinil, rufinamide

For updated information, please refer to <https://www.fda.gov/drugs/drug-interactions-labeling/drug-development-and-drug-interactions-table-substrates-inhibitors-and-inducers>

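### Section 5.6.2 tolerates up to 120 mL of grapefruit juice a day, while Appendix E lists grapefruit juice, without a volume limit, as a prohibited strong CYP3A4 inhibitor

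*Protocol*

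**What the plan says.** Four places in the protocol bear on grapefruit juice.

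- **Section 5.6.2 (Meals and Dietary Restrictions)** asks patients to avoid large amounts of grapefruit and Seville orange during the study. Its examples of a tolerated daily amount are "no more than a small glass of grapefruit juice (120 mL", or half a grapefruit, or 15 g of Seville marmalade. The same section requires a water-only fast from 2 hours before to 1 hour after each dose.
- **Appendix E (Prohibited CYP3A4 Inhibitors and Inducers)** names the juice itself in the strong-inhibitor cell: "elvitegravir and ritonavir, grapefruit juice, indinavir and ritonavir". That tier carries a potential rise in RXC004 exposure of more than 5-fold and the rule "These agents must not be given within 14 days of first dose of study treatment". The moderate tier (2- to 5-fold) has a required washout. Only the weak inhibitor tier (1.25- to 2-fold) is released: "These are not prohibited but should be used with caution". Juice appears in neither the moderate nor the weak tier.
- **Section 2.3.1.2** says that "strong and moderate CYP3A4 inhibitors are contraindicated in this protocol" and refers to Appendix E. If such a drug is unavoidable, RXC004 should be interrupted.
- **Section 5.6.3.1, item 3** says that use of some CYP3A4 inhibitors "should be restricted prior to first dose of study treatment and throughout the study treatment", and uses Appendix E as the list.

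Section 5.6.2 and Appendix E do not refer to each other.

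**The concern.** A site following Section 5.6.2 would tell a patient that a small daily glass of juice is acceptable. A site following Appendix E with Sections 2.3.1.2 and 5.6.3.1 would tell the patient to take none. Both instructions concern the same item, and nothing in the protocol ranks them.

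This matters because the protocol describes CYP3A4 as the only route of RXC004 metabolism, and the dose range has a known upper limit. At 3 mg, the next dose above 2 mg, "two DLTs of colitis and enteritis were observed in 2/4 (50%) evaluable patients", and that dose was declared non-tolerated. Section 2.3.1.2 also reports one Grade 3 enteritis among 12 patients in the sister study and one Grade 3 colitis among 21 patients in this study. Both patients were on 2 mg, and both events were considered related to RXC004.

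There is a smaller consequence for the PK objective. Section 6.4 asks for medicines, vaccines, vitamins and herbal supplements to be recorded. It does not mention dietary juice, so any effect on exposure could go untracked.

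**Working it through.** This is mainly a comparison of texts. The protocol gives no figure for the effect of 120 mL that could be reproduced.

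**Step 1: is it the same item?** Yes. Both Section 5.6.2 and Appendix E name grapefruit juice. Appendix E does not list whole grapefruit or Seville orange, so the conflict covers juice only.

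**Step 2: is it the same period?**
- Appendix E's explicit timing rule for strong inhibitors covers only the 14 days before first dose.
- The on-treatment restriction comes from Section 2.3.1.2 (contraindicated) and Section 5.6.3.1 (throughout treatment).
- Section 5.6.2 applies during the study, so it overlaps the on-treatment restriction.
- Section 5.6.3.2 uses the phrase *during the study* as including screening. If Section 5.6.2 means the same, the allowance also overlaps the 14-day window.

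**Step 3: is there an exception or a precedence rule?** None is written. Appendix E gives no volume threshold, and Section 5.6.2 does not present itself as an exception to Appendix E.

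**Step 4: does the fasting rule remove the conflict?** No. It keeps juice away from the dose but leaves the rest of the day open.

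**Step 5: exposure context.** The inputs are the steady-state geometric means in Table 9, for 3 mg and 2 mg monotherapy.

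| Parameter | 3 mg | 2 mg | Ratio |
|---|---|---|---|
| AUC0-24 | 2340 (n = 4, CV 32.5%) | 931 (n = 4, CV 61.1%) | 2340/931 = 2.51 |
| Cmin | 73.1 (n = 4) | 26.8 (n = 4) | 73.1/26.8 = 2.73 |
| Cmax | 220 (n = 4) | 68.5 (n = 5) | 220/68.5 = 3.21 |

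These ratios describe the distance between two dose groups. They do not say whether 120 mL of juice would close it, for three reasons.

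- No document gives an effect size for 120 mL.
- All three ratios lie inside the moderate tier (2- to 5-fold), so a moderate effect could fall on either side of the gap.
- The groups are small and variable. As an illustration, assume that the 61.1% is a geometric CV and that AUC is log-normal. The log-SD is then √ln(1 + 0.611²) = 0.563. At the weak-tier ceiling the 2 mg mean becomes 2 × 931 = 1862, and ln(2340/1862)/0.563 = 0.41. About 34% of patients would exceed the 3 mg geometric mean even under a 2-fold rise, which Appendix E permits.

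The starting dose also matters. The AUC gap to 3 mg is 2340/706 = 3.31 from 1.5 mg with nivolumab (n = 5), and 2340/392 = 5.97 from 1 mg (n = 3).

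**The case against.** The best defence is that the two texts can be harmonised. Section 5.6.2 is the specific, quantified rule for food. Appendix E speaks of drugs that are given, and is invoked under a list of prohibited concomitant medication where the verb is only that use be restricted. A volume cap is a kind of restriction, so the fault may be just a missing cross-reference. This fails on one point: Appendix E names the juice itself, so a diet-versus-drug division does not hold. The sponsor may have intended a small dietary exception, but none is written.

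Appendix E also points to an external regulatory table for updated information. Whether that table qualifies juice by amount cannot be checked here. Either way, it does not settle which of the protocol's own two rules a site should apply.

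Sites can ask. Section 5.6.3.1 sends questions on prohibited medication to the sponsor, and Section 6.4 adds that "The Medical Monitor should be contacted if there are any questions regarding concomitant or prior therapy". Toxicity is managed by dose interruption, dose reduction and the colitis guidance. These points stand and limit the consequence, but none supplies the answer.

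It is also fair to say that banning juice alone would sit oddly beside an untouched half-grapefruit allowance, since Section 5.6.2 offers the two as alternatives. That stands and is taken into the fix.

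**Conclusion.** The inconsistency is real and rests on the protocol's wording alone. Section 5.6.2 tolerates daily an item that Appendix E places, without qualification, in its strongest inhibitor tier, and that Sections 2.3.1.2 and 5.6.3.1 carry into the treatment period. It should be corrected. It does not touch the sample size or the primary analysis.

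Confidence is high for the conflict in the text. The clinical consequence is unquantified: harm is possible, not shown.

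A reader might infer more, and the documents do not support it:

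- *That 120 mL raises exposure more than 5-fold.* That figure is a potential effect stated for the whole strong tier, not for this volume of juice.
- *That the tier to which 120 mL belongs decides whether exposure stays below that at 3 mg.* The 2.5-fold AUC gap falls within the moderate tier and compares means from four patients per dose with wide spread, so no such conclusion follows.
- *That Appendix E alone bans juice on treatment.* Its timing rule is pre-dose; the on-treatment restriction depends on the other two sections.
- *That the half-grapefruit and marmalade allowances also contradict Appendix E.* Neither item is listed there.

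**What to change.** Delete the grapefruit juice allowance from Section 5.6.2. State that grapefruit juice is prohibited from 14 days before first dose until RXC004 discontinuation, with a cross-reference to Appendix E. In the same edit, the sponsor should decide whether the half-grapefruit and Seville marmalade allowances stay. Consistency with Appendix E does not require their removal, but Section 5.6.2 sets them as alternatives to the juice.

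Only if the sponsor holds data showing that 120 mL is a weak inhibitor of RXC004 clearance should it keep the allowance. It should then write that volume exception into Appendix E, for example in the weak tier, and cross-refer to it from Section 5.6.2.

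In either case, check that the patient information, which was not available for this review, carries the same rule.

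The cost is a minor dietary restriction for patients and a wording change. Screening runs from Day -28 to Day -1, so a 14-day juice-free interval can fit within it. Visits, sample size and the primary analysis are unaffected.
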